Appendix 1.3. Sample SAS Code for Analyses Described in Sections 8.1.2 – 8.2.6

Sample SAS code to fit the mixed model repeated measures specified in [Section 8.1.3](#) is given below. The response variable Y is the change from baseline at the study visits.

```
PROC MIXED DATA=xxx METHOD=REML EMPIRICAL;  
CLASS pid center trt visit genotype;  
MODEL y= ybase trt visit genotype trt *visit;  
RANDOM int/SUBJECT=center;  
  
REPEATED visit /SUBJECT= pid (center) r type=UN;  
  
RUN;
```

Sample SAS code for the survival analysis specified in [Section 8.1.2](#) is given below.

```
PROC LIFETEST DATA=xxx PLOTS=(s) graphics;  
TIME dur *status(0);  
STRATA trt;  
RUN;  
  
PROC PHREG DATA=xxx;  
MODEL dur*status(0)=trt genotype NYHAbase/ ties=EXACT;  
RUN
```

Sample SAS code for the ANOVA specified in [Section 8.1.4](#) is given below.

```
PROC GLM DATA=xxx;  
CLASS trt genotype NYHAbase;  
MODEL y= trt genotype NYHAbase trt*genotype trt*NYHAbase;  
RUN;
```

Sample SAS code for the Poisson regression specified in [Section 8.1.5](#) is given below.

```
PROC DATA=xxx;  
ln_styyr=log(styyr);* log transformation to normalize duration of participation ;  
RUN;  
  
PROC GENMOD DATA=xxx;  
CLASS trt genotype NYHAbase;  
MODEL y= trt genotype NYHAbase trt*genotype  
trt*NYHAbase/ type 3 dist=poisson link=log offset=ln_styyr;  
RUN;
```

Sample SAS code for the CMH test specified in [Section 8.1.6](#) is given below. In the code below, the variable NYHA_GENOTYPE is obtained from combining NYHA baseline classification and TTR genotype into one variable (with 4 levels).

```
PROC FREQ DATA=xx;
TABLES NYHA_GENOTYPE*TRT*STABILIZED / CMH
RUN;
```

Sample SAS code for the pattern mixture analysis specified in [Section 8.1.5](#) is given below.

```
PROC MIXED DATA=xxx empirical;
CLASS pid visit center trt pattern genotype;
MODEL y= ybase visit trt genotype pattern visit*trt
trt*pattern / solution;
random int/subject=center;
repeated visit /subject= pid (center) r type=UN;
ESTIMATE 'Tafamidis vs placebo Month 30'
trt 1 -1 visit*trt 0 0 0 0 0 0 0 1 -1
trt*pattern 0.5 0.5 -0.5 -0.5 /cl e; * Placebo adjusted LSMEANS of Tafamidis
averaged over the pattern (equal weight=0.5);
run;
```

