4.2. Statistical Decision Rules

All hypothesis testing will be conducted using two-sided tests with $\alpha = 0.05$ level of significance. The list of key-secondary endpoints and the methodology for controlling the study-level Type I error at 0.05 due to multiple analyses are detailed in [Section 8.2.2](#).

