8.1.3. Mixed Model Repeated Measures (MMRM) Analyses

The endpoints evaluated at multiple time points will be analyzed *using a mixed model repeated measures ANCOVA (MMRM) with an unstructured covariance matrix (or as appropriate); center and subject-within-center as random effects; treatment, visit, TTR genotype (variant and wildtype), and visit-by-treatment interaction, as fixed effects and Baseline score as covariate.* While the NYHA baseline classification may serve as an indicator of baseline severity, the endpoints that are evaluated at baseline (and at multiple points post-baseline) will use their respective baseline scores as the appropriate covariate for the MMRM analysis described above.

For the analyses by TTR genotype, the same model specified above will be used, with the addition of terms for TTR genotype-by-treatment interaction and TTR genotype-by-treatment-by-visit 3-way interaction. Similarly for dose, the same model specified above will be used with replacement of “dose” for “treatment”. Appropriate CONTRAST statements will be used to generate the LSMEANS from the MMRM model (eg, for dose, 20 mg vs placebo and 80 mg vs placebo) at each post-baseline study visit. The subgroup analysis by NYHA baseline classification (NYHA Classes I and II combined and NYHA Class III) will be done using ANCOVA (MMRM) with an unstructured covariance matrix (or as appropriate); center and subject-within-center as random effects; treatment, visit, TTR genotype (variant and wildtype), NYHA baseline classification, visit-by-treatment interaction, NYHA baseline classification-by-treatment interaction, NYHA baseline classification-by-treatment-by-visit 3-way interaction as fixed effects and baseline score as covariate. All the subgroup analyses will be considered exploratory.

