8.2.2. Key-Secondary Analyses

The key secondary endpoints listed below will be evaluated using a mixed model repeated measures ANCOVA detailed in [Section 8.1.3](#).

1. Change from Baseline to Month 30 in distance walked during the 6MWT;
2. Change from Baseline to Month 30 in KCCQ Overall score.

To maintain the type I error rate at or below the specified level, a pre-specified hierarchical order for testing as indicated above will be used to maintain the overall alpha at 0.05 for these two key secondary endpoints. The multiplicity procedure will be applied to the ITT analysis set only.

Statistical significance of the key-secondary analyses is dependent on first achieving statistically significant results in the primary analysis. In this hierarchical approach of key-secondary endpoints, the change from Baseline to Month 30 in distance walked during the 6MWT is first tested at the 0.05 level. If the p-value for the test of 6MWT is ≤ 0.05 , the 2nd variable in the list, the change from Baseline to Month 30 in KCCQ Overall Summary score will be tested at the 0.05 level. If the p-value of the test for 6MWT is > 0.05 , then statistical significance cannot be achieved for the subsequent test on KCCQ.

Supplemental analyses of the two key secondary variables will be performed to support the robustness of the conclusions drawn. The pattern-mixture analysis will group the subjects on the basis of their dropout or missing-data patterns. 'Patterns' will be defined under the following two cases:

Case 1:

Pattern 1A - all subjects who have provided the key-secondary endpoint (each done separately) data for month 30.

Pattern 1B - all subjects who have not provided the key-secondary endpoint data for month 30.

Case 2:

Pattern 2A - all subjects who have the key-secondary endpoint data (each done separately) for month 15 or beyond.

Pattern 2B - all subjects who do not have key-secondary endpoint data beyond month 15.

The pattern mixture analysis will use a mixed model repeated measures ANCOVA (MMRM) with an unstructured covariance matrix (or as appropriate); center and subject within center as random effects; treatment, visit, TTR genotype (variant and wild-type), pattern, visit by treatment interaction, and treatment by pattern interaction as fixed effects and baseline score as covariate. Sample SAS code is provided in [Appendix 1.3](#).

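### The only stated standard error for the 6MWT and KCCQ-OS models is an uncorrected sandwich summed over centres; unless centres are numerous, the 5% test of 6MWT rejects somewhat too often once the primary gate has opened

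*SAP*

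**What the plan says.** SAP 8.1.3 describes the repeated-measures model for 6MWT and KCCQ-OS "with an unstructured covariance matrix (or as appropriate); center and subject-within-center as random effects". It says nothing about how standard errors or denominator degrees of freedom are obtained, and neither does protocol 9.2.2.

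The only specification is the sample code in SAP Appendix 1.3. The procedure line is "PROC MIXED DATA=xxx METHOD=REML EMPIRICAL". The random effect is "RANDOM int/SUBJECT=center", the repeated effect is "REPEATED visit /SUBJECT= pid (center) r type=UN", and the mean model is "MODEL y= ybase trt visit genotype trt *visit", with no degrees-of-freedom option. The pattern-mixture block in the same appendix also requests the empirical variance and has the same random and repeated structure.

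On error control, SAP 4.2 states: "All hypothesis testing will be conducted using two-sided tests", at 0.05. SAP 8.2.2 sets a fixed order, 6MWT then KCCQ-OS, which "will be used to maintain the overall alpha at 0.05 for these two key secondary endpoints". It also sets a gate: "Statistical significance of the key-secondary analyses is dependent on first achieving statistically significant results in the primary analysis".

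**The concern.** With the random intercept on centre and subjects nested in centre, the fitted covariance is block-diagonal by centre. The sandwich then treats centres as the independent units. It is built from squared fitted residuals, which are too small on average, and with few units it is also a noisy estimate. Comparing the resulting statistic with a critical value near 1.96 ignores both problems.

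At stake is the level of the only two secondary endpoints with formal alpha control. If the code is followed as written, the 6MWT test can exceed 5% and its confidence intervals can be too narrow. If 6MWT is truly improved, the KCCQ-OS test that follows carries the same excess.

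**Working it through.** **Formula.** For centres c = 1 to C, with A = (Σ X_c′V_c⁻¹X_c)⁻¹ and fitted residuals r_c, the code's variance is A [Σ X_c′V_c⁻¹ r_c r_c′ V_c⁻¹X_c] A. The Mancl-DeRouen correction replaces r_c by (I − H_c)⁻¹ r_c, where H_c is the centre's leverage block. The model-based variance is A itself.

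**Inputs from the documents.** Two-sided 0.05 (SAP 4.2, 8.2.2); 160 placebo versus 80 + 160 = 240 pooled tafamidis (SAP 2.1); five post-baseline visits, Months 6 to 30 (protocol 7.7.4); the model in SAP 8.1.3 and Appendix 1.3; at least 30% in each genotype stratum (SAP 2.1), with 30% used.

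**Assumptions.** 20 to 100 centres of unequal size; centre intraclass correlation 0.03; 35% monotone missing by Month 30. The protocol's mortality assumptions alone give (0.25 × 160 + 0.125 × 240)/400 = (40 + 30)/400 = 17.5% missing.

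**Main check.** Null data, Month 30 contrast, known covariance, 5,000 trials per row; simulation standard error √(0.05 × 0.95/5000) = 0.3 points. The plan's own figure is the 5% level, and the model-based column recovers it. The corrected sandwich uses t on C − 1 degrees of freedom.

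| Centres | Code as written | Model-based | Corrected sandwich | Mean sandwich variance / true variance |
|---|---|---|---|---|
| 20 | 8.3% | 4.9% | 4.8% | 0.91 |
| 30 | 8.3% | 5.2% | 5.3% | 0.94 |
| 50 | 6.8% | 5.2% | 5.4% | 0.95 |
| 75 | 6.0% | 4.9% | 4.8% | 0.97 |
| 100 | 5.6% | 4.9% | 4.9% | 0.99 |

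Fifty equal-sized centres give 6.2% with the code as written.

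**Cause.** Clustering the same sandwich on subjects gives 5.3 to 5.4%, so the excess comes from clustering on centre. Bias alone does not explain it: at 20 centres, 2[1 − Φ(1.96 × √0.908)] = 6.2%, against 8.3% simulated. The rest is instability of the estimate, so the degrees of freedom matter too. Rescaling by C/(C − 1) with t on C − 1 degrees of freedom repairs only part: 6.0, 6.6, 6.1, 5.4 and 5.2% down the rows.

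**Covariance estimated by REML.** At 25 centres (1,000 trials) the code as written gives 9.2%, model-based 6.0% and the corrected sandwich 6.1%. At 50 centres (1,500 trials) the figures are 7.2%, 5.5% and 6.1%. Simulation standard error is 0.6 to 0.9 points. The gap between the code and model-based errors on the same data is 9.2 − 6.0 = 3.2 and 7.2 − 5.5 = 1.7 points. Kenward-Roger degrees of freedom were not simulated.

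**Simpler set-ups** (one time point):
- 280 subjects, intraclass correlation 0.05: 8.4, 7.5 and 6.2% at 25, 40 and 60 centres (model-based 5.2, 5.0 and 4.4%).
- The same size with zero centre effect: 8.0, 7.2 and 6.0% (model-based 5.3, 5.4 and 4.7%). No real centre effect is needed.
- 320 subjects, correlation 0.03: 8.1, 6.4, 5.9 and 6.5% at 25, 50, 75 and 100 centres (model-based 4.9 to 5.5%, corrected sandwich 4.5 to 5.5%).

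**Primary gate.** Taking the 90% power stated in protocol 9.1 (400 subjects, 30% mortality reduction) and treating the two tests as independent, the unconditional 6MWT error is 0.90 × 8.3% = 7.5% at 20 centres, 0.90 × 6.8% = 6.1% at 50 and 0.90 × 5.6% = 5.0% at 100. Under the global null the primary succeeds at most 5% of the time, so false key secondary claims cannot exceed 5%.

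**Unequal arm variances.** The code fits one covariance to both arms. Survivors under the protocol's assumptions are 160 × 0.75 = 120 and 240 × 0.875 = 210. If placebo variance is 1.5 times tafamidis variance, the true variance of a simple difference is 1.5/120 + 1/210 = 0.01726. The pooled-variance version is [(120 × 1.5 + 210)/330] × (1/120 + 1/210) = 0.01548. The ratio is 0.897, and the model-based test has level 2[1 − Φ(1.96 × √0.897)] = 6.3%. Simulation with these numbers gave 6.2 to 6.9% over 30 to 100 centres, against 7.5 to 5.9% for the code as written. The 320-subject set-up at the same variance ratio gave 5.2 to 6.0% model-based and 4.0 to 5.0% for the corrected sandwich.

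**The case against.** The strongest reply has four parts.

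1. **It is sample code.** The appendix is labelled so and is visibly unfinished: the main block has no contrast statement, although SAP 8.1.3 says contrasts will be used. A missing degrees-of-freedom option is thus weak evidence of a settled decision. This stands in part. But nothing else sets the standard error, and SAP section 1 records corrections to this code in Amendments 1 and 4, so it is maintained as specification.

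2. **The number of centres is unknown.** An international trial in a rare disease may have many small sites. This stands. At 100 centres the main check gives 5.6%, close to simulation error. A reader might infer that the tests certainly reject too often by about three points; the documents do not support that, because they give no centre count.

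3. **A robust variance has a purpose.** This stands. A reader might infer that the unstructured covariance already makes model-based errors valid, so that the empirical option should simply be deleted. That does not follow: the covariance is common to both arms, the text allows another structure, and unequal variances with unequal arms lift the model-based level as well. Kenward-Roger degrees of freedom do not repair a wrong covariance. The sound complaint is the missing correction, not the use of a sandwich.

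4. **The gate protects.** It does so fully under the global null, and only partly when the primary effect is real.

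**Conclusion.** The point holds in a limited form. As written, the code yields a test of 6MWT whose level, given an open gate, is about 8% at 20 to 30 centres, 6 to 7% at 50 to 75 and roughly 5.5 to 6.5% at 100. The direction was the same in every set-up and at every centre count tried. The size rests on assumed centre numbers, centre sizes, intraclass correlation and missingness, none of which the documents supply.

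A reader might infer that the promise of 5% fails outright. It fails only when the primary effect is real and 6MWT, or KCCQ-OS after a true 6MWT effect, is null. If both are null, the family-wise excess is that of the 6MWT test alone. The primary Finkelstein-Schoenfeld test is not affected.

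Both remedies held 5% when the covariance was known. With REML they came out at 5.5 to 6.1%, within about two simulation standard errors of 5%, so the margin of repair is less certain there.

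**What to change.** In SAP 8.1.3 and both PROC MIXED blocks of Appendix 1.3, replace the uncorrected sandwich by one pre-specified estimator, and state the expected number of centres. Either choice is defensible:

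- a bias-corrected sandwich (for example Mancl-DeRouen) with degrees of freedom based on the number of centres, which also tolerates unequal variances between arms; or
- model-based standard errors with DDFM=KR and the unstructured covariance fixed in advance.

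Report the other as a sensitivity analysis. Before finalising, simulate the chosen estimator at the actual centre sizes with the covariance estimated.

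The cost is a sentence or two in 8.1.3 and edits to two code blocks, with no new data; the SAP describes the study as still blinded. The corrected sandwich may need extra programming, which should be checked. Intervals may be slightly wider, and the model-based option relies on the common covariance being right.

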7.7.1.1. Kansas City Cardiomyopathy Questionnaire

The KCCQ ([Appendix 1.1](#)) (Green 2000)¹⁹ is a 23-item subject-completed questionnaire that assesses health status and health-related quality of life in subjects with heart failure. Items assess the ability to perform activities of daily living, frequency and severity of symptoms, the impact of these symptoms, and health-related quality of life. Response options vary by question. Scoring yields scores for 6 domains (Physical limitation, Symptom stability, Symptoms, Self-efficacy, Social limitation, and Quality of life), two summary scores (Functional summary and Clinical summary), as well as an Overall Summary score. Domain scores are transformed to a 0 to 100 range; higher scores indicate better health status. It takes approximately 4-6 minutes for a subject to complete the KCCQ.

Subjects will complete the KCCQ at the Baseline visit and at Months 6, 12, 18, 24, and 30 (or Early Study Discontinuation) as listed in the [Schedule of Activities](#). In each instance of administration, the KCCQ should be completed by subjects before completing the EQ-5D-3L ([Appendix 2](#)) and PGA assessments([Appendix 3](#)).

The KCCQ can be found in [Section Appendix 1.1](#).

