7.7.3. Diflunisal Concentration

After the recording of ECGs, Echocardiograms and blood pressure, a blood sample will be collected to determine if the subject has taken diflunisal. The blood sample for this assessment will be taken at Screening, Baseline and Months 1, 6, 18, and 30. Use of diflunisal during the study is not permitted. Subjects taking diflunisal will be appropriately counselled. Such subjects will be handled as protocol violators in the analysis as described in the Statistical Analysis Plan.

Samples will be analyzed using a validated analytical method in compliance with Pfizer standard operating procedures.

Detailed instructions for collection, storage, labeling, and shipment of all samples are provided in a separate study laboratory manual.

7.7.4. 6-Minute Walk Test (6MWT)

A 6MWT will be conducted during the Screening period and at the Baseline visit and at Month 6, 12, 18, 24, and 30 visits (or Early Study Discontinuation). There will be one 6MWT during the Screening period. Subjects who are unable to walk 100 meters at Screening will be considered a Screen Failure.

The test will be conducted in accordance with guidelines established by the American Thoracic Society.

Detailed instructions for conducting the 6MWT are provided in [Section Appendix 4](#).

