Appendix 1.2. Definition and Use of Visit Windows in Reporting

The following describes the clinical visits windows allowed within the protocol after month 1 visit:

Clinic Visits (Months 3, 6, 9, 12, 15, 18, 21, 24, 27, 30) ± 2 weeks

End of Study Visit (Month 30) ± 2 weeks or Early Study Discontinuation

However, in order to maximize the use of all available data, the visit windows for each visit are expanded as follows:

For endpoints collected every 3 months:

Clinic Visits (Months 3, 6, 9, 12, 15, 18, 21, 24, 27, 30) ± 6 weeks

All nominal visits (months 3, 6, 9, 12, 15, 18, 21, 24, 27, 30) will use the data as collected from that visit. Early termination visits will never replace an existing visit. If the visit covered by the windowing rules above is already populated with an existing nominal visit, then the early termination visit should be mapped forward to the next 3 month visit.

For endpoints collected every 6 months:

Clinic Visits (Months 6, 12, 18, 24, 30) ± 3 months

All nominal visits (months 6, 12, 18, 24, 30) will use the data as collected from that visit. Early termination visits will never replace an existing visit. If the visit covered by the windowing rules above is already populated with an existing nominal visit, then the early termination visit should be mapped forward to the next 6 month visit.

For Echocardiogram collected at months 6, 18, and 30:

Clinic Visits (Months 6, 18, 30) ± 6 months

All nominal visits (months 6, 18, 30) will use the data as collected from that visit. Early termination visits will never replace an existing visit. If the visit covered by the windowing rules above is already populated with an existing nominal visit, then the early termination visit should be mapped forward to the next nominal visit.

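### Does the sample pattern-mixture ESTIMATE line, one coefficient short as read, call for a change to the SAP?

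*SAP*

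**What the plan says.** SAP Section 8.2.2 plans a supplemental pattern-mixture analysis for each key secondary endpoint, change to Month 30 in 6MWT and in KCCQ-OS. It defines two pairs of patterns. Case 1 splits subjects by whether they have Month 30 data, and Case 2 by whether they have data around or after Month 15. It lists the fixed effects, random effects and covariance, and refers to Appendix 1.3 for sample code.

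The code declares "CLASS pid visit center trt pattern genotype" and labels its contrast as tafamidis versus placebo at Month 30. The coefficients begin "trt 1 -1 visit*trt 0 0 0 0 0 0 0 1 -1" and end with four `trt*pattern` values (0.5, 0.5, -0.5, -0.5). A comment says the result is "averaged over the pattern (equal weight=0.5" for each pattern. The block is introduced by "Sample SAS code for the pattern mixture analysis specified in", followed by a reference to Section 8.1.5.

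The visit schedule is consistent across the documents. For KCCQ, Protocol Section 7.7.1.1 has "Subjects will complete the KCCQ at the Baseline visit and at Months 6, 12, 18, 24, and 30". For 6MWT, Protocol Section 7.7.4 has "at the Baseline visit and at Month 6, 12, 18, 24, and 30 visits". SAP Appendix 1.2 windows the six-monthly endpoints as "Clinic Visits (Months 6, 12, 18, 24, 30) ± 3 months".

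**The concern.** Nine values cannot fill a `visit*trt` table with two arms, because two times any number of visits is even. If the line were run as it stands, the +1 and -1 would fall on the wrong cells and the procedure would report the contrast as non-estimable.

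SAP Section 7 imputes nothing in the MMRM analyses and reserves multiple imputation for the primary analysis. The pattern-mixture model is therefore the only planned missing-data check on 6MWT and KCCQ-OS. If its one declared contrast failed, that check would be empty. The wrong section number adds to the impression of a block that was not proofread.

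**Working it through.** **Inputs.** There are five post-baseline visits: Months 6, 12, 18, 24 and 30 (Protocol 7.7.1.1 and 7.7.4; SAP Appendix 1.2). The response is change from baseline, so baseline is not a visit level (Appendix 1.3). There are two arms, pooled tafamidis and placebo (SAP 8.2.2), and two patterns in each case.

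**Count.** `trt` needs 2 values and has 2. `trt*pattern` needs 2 x 2 = 4 and has 4. `visit*trt` needs 5 x 2 = 10 and has 9: seven zeros, 1 and -1.

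**Where the values fall.** The CLASS statement lists visit before trt, so arm changes fastest. An omitted trailing value counts as zero.

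| Position | Cell | As read | With eight leading zeros |
|---|---|---|---|
| 1 to 7 | Month 6, arm 1, through Month 24, arm 1 | 0 | 0 |
| 8 | Month 24, arm 2 | +1 | 0 |
| 9 | Month 30, arm 1 | -1 | +1 |
| 10 | Month 30, arm 2 | 0 (by default) | -1 |

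**Estimability.** Every row of the design has a single 1 in each term. In an estimable contrast, therefore, the `visit*trt` values for an arm must sum to that arm's `trt` value, and those for a visit must sum to that visit's `visit` value.

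- As read: arm 1 sums to -1 against a `trt` value of +1, and arm 2 sums to +1 against -1. Month 24 sums to +1 and Month 30 to -1, while no `visit` values are given. All four conditions fail.
- With eight zeros: arm 1 sums to +1, arm 2 to -1 and Month 30 to 0, all as required. The `trt*pattern` values also agree: 0.5 + 0.5 = 1 for arm 1, -0.5 - 0.5 = -1 for arm 2, and 0.5 - 0.5 = 0 within each pattern.

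The ten-value line remains estimable when pattern B has no Month 30 data. The model has no visit-by-pattern term, so within an arm the Month 30 mean for pattern B equals the Month 30 mean for pattern A plus the B-minus-A difference at Month 6. That holds in Case 1 and in Case 2, where pattern 2B has Months 6 and 12 only.

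**Numerical confirmation.** A rank test on the full fixed-effects design gave the same answer with all cells filled, in Case 1 and in Case 2: nine values not estimable, ten values estimable. In a noise-free example under Case 1, two equally valid least-squares solutions gave -1.19 and 0.71 for the nine-value line. Both gave -1.37 for the ten-value line, and -1.37 was the true difference.

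**Class order.** The main MMRM code in the same appendix uses "CLASS pid center trt visit genotype", with trt before visit. Under that order the eight-zero line would also fail. The pattern-mixture block prints its own order, so this matters only if someone mixes the two blocks.

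**Cross-reference.** Section 8.1.5 is Poisson regression, and the pattern-mixture analysis is in 8.2.2. Section 8.2.2 itself points correctly to Appendix 1.3.

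**The case for a change.** The best argument for amending is that it costs one character and one section number, and that the sponsor has treated this statement as worth correcting. The Amendment 4 table in SAP Section 1 records a fix to an error in the ESTIMATE statement of this sample code. The Amendment 1 table ties the code to a May 2014 agreement with FDA. On that view the agreed contrast ought to run as printed, the more so because it is the only missing-data check on the two key secondary endpoints.

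The count and the wrong cross-reference stand. The step from there to a change in the plan does not:

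- The snippets are illustrations with placeholder data set names. Others in the appendix would not run as read either: the Poisson block has a PROC statement with no procedure name, and the Cox and CMH blocks each lack a semicolon. Production programs have to be written and checked in any case.
- The estimand does not rest on the coefficient string. The label gives the comparison and the visit, the comment gives the weights, and 8.2.2 gives the model and the patterns. With the printed CLASS order, only eight leading zeros deliver that contrast.
- The error announces itself. A non-estimable flag cannot be mistaken for a result.
- A single zero in a run of identical characters is easily lost when a PDF is read by machine. The Amendment 4 entry shows that the statement was revisited, but it does not settle whether the SAP page has nine values or ten.

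The equal weighting of the two patterns is also open to debate. It is a declared choice and no bias from it has been shown, so it does not turn a slip in the code into a fault in the plan.

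**Conclusion.** This is a clerical slip at most, and no change to the plan is needed. As read, one of ten `visit*trt` coefficients is missing and one section number is wrong. The analysis is supplemental and carries no alpha, and its target is fixed by the label, the comment and Section 8.2.2. The programmer will supply the zero, or take the Month 30 difference of the `visit*trt` least-squares means, which has the same coefficients. The Finkelstein-Schoenfeld primary test, the main MMRM tests of 6MWT and KCCQ-OS and their hierarchical order are untouched, and no planned conclusion changes.

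This rests on five post-baseline visits and two arms, which the documents support, and on the printed CLASS order. Whether the zero is absent from the SAP page itself cannot be told from the text available. The verdict is the same either way.

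### The pattern-mixture check on 6MWT and KCCQ-OS weights each missing-data pattern one half in both arms, so a difference between arms in the pattern shares cannot enter its estimate

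*SAP*

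**What the plan says.** SAP 8.2.2 plans pattern-mixture models for the two key secondary endpoints, the Month 30 changes in 6MWT and KCCQ-OS. Their purpose is stated: "Supplemental analyses of the two key secondary variables will be performed to support the robustness of the conclusions drawn". SAP Section 7 names no other missing-data analysis for these endpoints.

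Two definitions of pattern are used in turn. In Case 1 the incomplete group is "Pattern 1B - all subjects who have not provided the key-secondary endpoint data for month 30". In Case 2 it is "Pattern 2B - all subjects who do not have key-secondary endpoint data beyond month 15". Neither separates death from withdrawal. The model adds to the MMRM "pattern, visit by treatment interaction, and treatment by pattern interaction as fixed effects and baseline score as covariate".

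SAP 8.2.2 gives no rule for combining the patterns. The only rule is in the ESTIMATE statement of SAP Appendix 1.3, where the coefficients are "trt*pattern 0.5 0.5 -0.5 -0.5". No coefficient is placed on the pattern main effect, and the comment beside the statement confirms equal weights: "averaged over the pattern (equal weight=0.5").

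**The concern.** A pattern-mixture estimate of the treatment effect among all randomized subjects averages the patterns within each arm in proportion to the subjects they hold. Fixed halves do something else. A small group with little data can supply half of the answer, and both arms are treated as if they had the same split. If placebo subjects die or leave more often, and those subjects walk less far or score lower, that contribution to the arm difference is lost.

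What is at stake is the robustness statement for the two alpha-controlled secondary claims. The check could disagree with the MMRM, or agree with it, because of the weights and not because of what missing data did to the result.

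**Working it through.** **Inputs.** Pattern weights of 0.5: SAP Appendix 1.3. Arms of 240 (80 + 160 pooled tafamidis) and 160 (placebo): SAP 2.1. Mortality of 12.5%, or 17.5% in the conservative case, against 25%: Protocol 9.1. These mortality figures serve as a lower bound on the Pattern B shares. Everything else below is assumed and marked so.

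**Step 1: what the code estimates.** Let dA be the Month 30 effect in Pattern A, gT and gP the B-minus-A gaps on tafamidis and placebo, and qT and qP the Pattern B shares.

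- Coded contrast: dA + 0.5(gT − gP).
- Effect in the randomized mix: dA + qT·gT − qP·gP.
- Coded minus mix: (0.5 − qT)gT − (0.5 − qP)gP.

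Rebuilding the design matrix reproduces the coded contrast exactly as a 50:50 average of Month 30 cell means in each arm, given eight leading zeros in the visit-by-treatment coefficients. The text as supplied has seven, "trt 1 -1 visit*trt 0 0 0 0 0 0 0 1 -1". Five visits by two arms need ten entries, so a zero may have been lost in extraction, and nothing here rests on it.

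**Step 2: point estimate.** Assume dA = 30 m and the gaps shown. Each cell gives coded / mix, in metres.

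| qT / qP | gT = gP = −40 | gT = −60, gP = −40 | gT = −20, gP = −40 |
|---|---|---|---|
| 5% / 5% | 30.0 / 30.0 | 20.0 / 29.0 | 40.0 / 31.0 |
| 12.5% / 25% | 30.0 / 35.0 | 20.0 / 32.5 | 40.0 / 37.5 |
| 17.5% / 25% | 30.0 / 33.0 | 20.0 / 29.5 | 40.0 / 36.5 |
| 50% / 50% | 30.0 / 30.0 | 20.0 / 20.0 | 40.0 / 40.0 |

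For example, 30 + 0.125(−40) − 0.25(−40) = 35.0. When the gaps are equal, the coded line returns dA whatever the shares. With unequal gaps it can fall below or above the mix.

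**Step 3: where the Pattern B information comes from.** The model has no pattern-by-visit term. Pattern 2B has no values beyond Month 15, and 6MWT and KCCQ are scheduled at Months 6 and 12 before then, so its Month 30 level is extrapolated and still carries half the weight. Pattern 1B lacks only Month 30 and may have data up to Month 24.

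**Step 4: precision.** Generalized least squares for visit, treatment-by-visit, pattern and treatment-by-pattern at Months 6 to 30. Assumed: AR(1) correlation 0.75 between six-month visits, SD 90 m, Pattern A complete, Pattern B exits spread evenly over the earlier visits, no centre effect, model-based standard errors. The deaths-only shares for Case 2 use a constant hazard to Month 15: 1 − 0.875^0.5 = 6.5% and 1 − 0.75^0.5 = 13.4%, or 0.6 × 6.5 + 0.4 × 13.4 = 9.2% overall. For Case 1, deaths alone give 0.6 × 12.5 + 0.4 × 25 = 17.5% overall.

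| Scenario (tafamidis / placebo) | Equal-weight SE | Arm-specific SE | Ratio, shares fixed | Ratio, shares estimated |
|---|---|---|---|---|
| Case 2, deaths only | 17.1 | 9.84 | 1.74 | 1.71 |
| Case 2, 15% / 20% | 14.20 | 10.35 | 1.37 | 1.34 |
| Case 2, 20% / 30% | 13.37 | 11.00 | 1.22 | 1.18 |
| Case 1, deaths only | 13.26 | 10.15 | 1.31 | 1.27 |
| Case 1, 30% / 40% | 11.99 | 11.14 | 1.08 | 1.04 |
| Case 1, 40% / 60% | 12.58 | 12.63 | 1.00 | 0.97 |

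The last column adds gT²qT(1 − qT)/240 + gP²qP(1 − qP)/160 to the arm-specific variance, with gT = gP = −60 m assumed. For Case 1, deaths only: 3600 × (0.125 × 0.875/240 + 0.25 × 0.75/160) = 5.9, so the SE is √(10.15² + 5.9) = 10.4 and the ratio is 13.26/10.4 = 1.27. With fixed shares the ratio does not depend on the SD.

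**The case against.** The best defence is that the choice is open and was revisited. The comment in the code states it. The SAP amendment history ties the analysis and its code to an agreement with FDA, and it records a later correction to the ESTIMATE statement. That deserves weight, but the history does not say that the agreement covered the weights.

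It is also fair that this is sample code for a supplemental analysis carrying no alpha. The solution option prints the pattern coefficients, so a share-weighted point estimate could be assembled by hand. Its standard error could not be obtained from those coefficients alone, and no such estimate is prespecified.

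Several stronger readings are tempting and are not supported:

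- A reader might infer that the contrast describes no real population. It matches the randomized mix if each arm splits 50/50, or if neither arm has a gap between patterns.
- A reader might infer that it ignores dropout. It carries half the treatment-by-pattern difference, 0.5(gT − gP). Only the difference in shares is lost.
- A reader might infer that it is the sole supporting analysis. The key secondary endpoints are also analysed on the per-protocol set (SAP 5, SAP 8.2 and the footnote to Table 2), and two pattern definitions are run.
- A reader might infer that equal weights always cost precision. The loss disappears as Pattern B nears half of subjects, and at 40%/60% the share-weighted estimate is slightly the less precise once share uncertainty is counted.

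One objection stands in full. Pattern B mixes deaths with withdrawals, so any average over it, equal or share-weighted, includes notional Month 30 values for subjects who have died.

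**Conclusion.** The point holds for the weighting rule. Fixed halves in both arms remove any difference in pattern shares from the estimate, and the protocol's planning assumptions already imply such a difference. The size cannot be fixed from the documents, which give no dropout rate. The visit windows in SAP Appendix 1.2 also let some early-termination values count as Month 30, which moves subjects between patterns. Under the stated assumptions, the standard-error ratio runs from 1.74 to about 1.0 with shares treated as fixed, and from 1.71 to 0.97 with share uncertainty and a 60 m gap. The upper end rests on deaths being the only source of Pattern 2B. The bias has no fixed sign.

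A reader might infer that the key secondary results themselves are in doubt. They are not: the primary test and the MMRM hierarchy do not use this contrast. The change is worth making because it corrects, at little cost, the only missing-data check on these endpoints.

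**What to change.** State in SAP 8.2.2 and Appendix 1.3 that the patterns are weighted by their observed shares within each arm, and name the denominator. The contrast becomes `trt*pattern (1−qT, qT, −(1−qP), −qP)` with `pattern (qP−qT, qT−qP)`. With shares of 12.5% and 25% this is `trt*pattern 0.875 0.125 −0.75 −0.25` and `pattern 0.125 −0.125`, which is estimable. Take the standard error by the delta method or a subject-level bootstrap so that it allows for the estimated shares. Keep the equal-weight line as a secondary estimate, and base the robustness statement on the share-weighted one. Report the share of subjects in each pattern by arm beside both.

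The cost is a revised ESTIMATE statement and one extra computing step, specified before unblinding. The downside is some added variance from the estimated shares. How deaths should enter a Month 30 comparison needs its own statement, because reweighting does not settle it.
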